Research illustrates that early bonding between parent/caregiver leads to improved outcomes of the infant suffering from NAS. This demonstration projects allows for a greater participation of the mother in the care of her infant while inpatient. It will also empower her to better understand the nature of neonatal drug withdrawal, to recognize its signs in a timely fashion and to provide better non-pharmacological care for her infant with proven comfort and feeding techniques.

The project will also provide home support and close monitoring as well as regular developmental follow-up for these infants through our JHACH NICU follow-up clinic, hence identifying and quickly responding to delays. These infants are prone to have developmental issues and recent research is demonstrating they have problems upon entering the school systems at age 4 and 5 years. While we have follow-up clinics in St Petersburg and Sarasota, the current Medicaid system and Medicaid HMO's are not funding these infants to come to the clinics, as they are considering it primary care. JHACH NICU follow-up clinic is much different than primary care, is multidisciplinary and offers standardized psychometric testing and referrals for services as deemed indicated.

4. Inclusion/Exclusion Criteria for Mother/Baby dyad

Methadone Treatment Group:

Inclusion criteria

- 1) Baby is diagnosed with neonatal abstinence syndrome;
- 2) Mother under the care of Operation PAR;
- 3) Mother resides in Pinellas or Pasco county at the time of enrollment and is expected to throughout the infant's methadone treatment period;
- 4) Mother has been deemed by PAR officials as being compliant with the detoxification program;
- 5) Mother has completed induction methadone treatment and has had no changes in medication dosage of 10% or greater in the two weeks preceding delivery;
- 6) Mother has been prescreened and deemed adequate candidate by the demonstration project team members;
- 7) No known concerns from Florida Department of Children and Families (DCF) regarding the infant's ability to return to the home;
- 8) Newborns ≥ 37 0/7 weeks gestation;
- 9) Newborns transferred to JHACH within 72 hours from birth;
- 10) Newborns ≥ 2.5 kg weight at birth; Informed parental consent.

Principal Investigator: [name], MPH

Application Number: IRB00107690

Exclusion Criteria

- 1) Major congenital anomalies;

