- 2) Major concomitant medical illness including planned antibiotic treatment for greater than 3 days or NPO status;
- 3) Infants who are being placed for adoption;
- 4) Infants in significant pain requiring narcotic medication for comfort (for example those with a fracture);
- 5) Infants whose maternal UDS at the time of delivery is positive for any other drug of abuse beside opiates;
- 6) Mother with hearing or language impairment.

Comparison Group:

Inclusion Criteria:

- 1) Baby is diagnosed with neonatal abstinence syndrome;
- 2) Newborns \geq 37 0/7 weeks gestation;
- 3) Newborns transferred to JHACH within 72 hours from birth;
- 4) Newborns \geq 2.5 kg weight at birth;
- 5) Informed parental consent.

Exclusion Criteria:

- 1) Infant not requiring pharmacologic treatment for NAS;
- 2) Major congenital anomalies;
- 3) Major concomitant medical illness including planned antibiotic treatment for greater than 3 days or NPO status;
- 4) Infants who are being placed for adoption;
- 5) Infants in significant pain requiring narcotic medication for comfort (for example those with a fracture);
- 6) Mother with hearing or language impairment;
- 7) Infants known upon admission who will be placed into state custody or sheltered.

Principal Investigator: [name], MPH

Application Number: IRB00107690

Study Procedures

- a. **Study design, including the sequence and timing of study procedures** (distinguish research procedures from those that are part of routine care).

General Design Issues:

The proposed demonstration project is a non-randomized, un-blinded feasibility study. A prospective cohort study design will be implemented.

Eligibility and Enrollment Process:

a) **Methadone Treatment Group:** Mothers who meet the criteria for enrollment in the demonstration project will be identified by the Operation PAR personnel during the last month of pregnancy. Such individuals will be approached by PAR personnel to determine their willingness to learn more about the methadone study. If they are interested, their contact information will be given to a study team member at Kids Home Care. The Kids Home Care study team member will contact the mother via telephone to discuss the study and may provide mother with a copy of the informed consent in order to give the mother ample time prior to delivery to ask questions of the study team.

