JHACH NICU Stork Nurses communicate with the Bayfront Baby Place Nurses a minimum of two times per day to check for potential NAS infants and transfers. Such communication readily identifies candidate mother / infant dyads shortly after delivery, and the pre-qualified mother will be approached for consent by a member of the study team (MD or mid-level).

b) **Comparison Group:** Mothers of infants who are admitted to the JHACH NICU with the diagnosis of NAS and who are started on treatment with a narcotic different than methadone, will be identified during the first week of NICU admission. Those mothers will be approached for consent by a member of the study team.

The difference between the two groups is further delineated in the tables below.

NOTE regarding screen failures:

Up to 35% of infants with NAS do not require pharmacological treatment as their symptomatology is controlled by non-pharmacological interventions. Such infants are released home after an observation period of about 7 days. If a patient was consented for either the comparison or methadone group and did not require pharmacological treatment for NAS, these infants will be considered screen failures. Accordingly, there will be no measures of bonding and depression, no outpatient follow-up by either KHC or the JHACH pediatrician and no assessment of development.

Principal Investigator: [name], MPH

Application Number: IRB00107690

Study Design:

Study Schedule of Events:

a) Methadone Treatment Group

Study Intervention	Enrollment	While inpatient	After discharge home on methadone	6 – 8 weeks of age	4 months of age	8 months of age	12 months of age
Informed Consent	X						
Methadone Administration		X ^a	X ^b				
Child Protective Investigator (CPI) clearance of the home		X (prior to discharge)					
Social Work Home Assessment			X (upon discharge)				
Face-to-face teleconferencing			X ^c				
Finnegan scoring		X	X ^b				
Kids Home Care Visit			X ^b		X ^f	X ^f	X ^f
JHACH Outpatient Pediatrician H&P, PE			X ^d				
The Postpartum Bonding Questionnaire (PBQ)		X ^e		X ^f			
Edinburgh Postnatal Depression Scale (EPDS)		X ^e		X ^f			
Ages And Stages Questionnaire (ASQ)					X	X	X

^a Per protocol

^b Twice daily until 48 hours after total weaning of medication is achieved

^c Every 3-4 hours until 48 hours after total weaning of medication is achieved

^d Within 1-2 days after discharge then weekly for 4 weeks until discontinuation of methadone treatment

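### Only methadone-group mothers must pass a compliance and suitability judgement, and dyads that fail it can become comparators, so the unadjusted LOS comparison can tilt towards methadone

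*Combined protocol and SAP*

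**What the plan says.** Section 4 of the combined protocol and SAP sets two judgement-based entry conditions for the methadone group. Inclusion 4 reads "Mother has been deemed by PAR officials as being compliant with the detoxification program". Inclusion 6 reads "Mother has been prescreened and deemed adequate candidate by the demonstration project team members". The protocol gives no items, checklist, timing or decision record for inclusion 6.

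The comparison-group criteria in the same section contain no maternal compliance or suitability condition. Their nearest exclusion, number 7, covers infants known on admission to be going into state custody or shelter.

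Under Eligibility and Enrollment Process, methadone candidates "will be identified by the Operation PAR personnel during the last month of pregnancy". Comparators are mothers of NICU infants with NAS "who are started on treatment with a narcotic different than methadone, will be identified during the first week of NICU admission", and "Those mothers will be approached for consent by a member of the study team". Standard care in this NICU is morphine with clonidine as adjunct (section 3), which is a narcotic other than methadone.

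General Design Issues states: "The proposed demonstration project is a non-randomized, un-blinded feasibility study". Section 6c compares LOS by t-test or Wilcoxon rank sum test, with no covariate adjustment, matching or restriction.

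**The concern.** The two groups pass through different filters, and the difference lies in maternal characteristics that plausibly affect the outcomes. The Abstract argues that an absent caregiver lengthens the hospital stay, and section 3 links early bonding to better infant outcome. A prescreen for a programme built on bedside presence and home care will plausibly favour engaged, stable mothers.

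The filter can act twice. It removes mothers with a less favourable outlook from the methadone group, and nothing stops those same dyads from entering the comparison group. Both effects push LOS, bonding, depression and readmission in favour of methadone, whatever methadone itself does. No planned analysis would reveal or correct this, and without a log of decisions a reader could not judge how strong the selection was.

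**Working it through.** **1. Can a turned-down dyad become a comparator?** Take a PAR mother who fails inclusion 4 or 6 and whose term infant of adequate weight needs drug treatment. The infant receives standard care, which is not methadone, and so fits the comparison-group definition. None of the seven comparison exclusions names PAR mothers or dyads turned down for methadone. Exclusion 7 removes her only if custody or shelter placement is already known. She can be approached.

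**2. The plan's own sample size.** Inputs from section 6c: 25 per group, SD 5 days, difference 4 days, alpha 0.05, power 80%.
- n per group = 2 × (1.96 + 0.842)² × 5² / 4² = 24.5, rounded up to 25.
- Power at n = 25 is 80.7% (normal) or 79.1% (noncentral t).

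The stated figure reproduces as a two-sided calculation.

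**3. Share of the comparison pool that could be unentered PAR dyads.** Inputs from Accrual: an average of 131 treated NAS infants, read as per year; about 30% PAR; 25 methadone places. Assumption: accrual takes one year.
- PAR dyads: 131 × 0.30 = 39.3. Non-PAR: 131 × 0.70 = 91.7.
- PAR dyads not entered: 39.3 − 25 = 14.3.
- Share of the pool: 14.3 / (14.3 + 91.7) = 13.5%.

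This counts every unentered PAR dyad as turned down, which overstates it. Some would be lost to gestation, weight, transfer time or anomalies, which exclude from both groups, and others to polydrug use or refusal. It also assumes that enrolled comparators reflect the pool; the plan does not say how mothers within it are chosen. Longer accrual would raise the share, but never above the 30% PAR share.

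**4. Shift and false-positive rate.** Let q be the share of comparators who would have failed the prescreen and d the extra days their infants stay. The spurious difference is q × d. The documents do not give d, so 2, 3 and 5 days are assumptions. With no true effect, the two-sided t-test rejects with probability P(|T| > 2.011), where T is noncentral t on 48 df with noncentrality shift / (5 × √(2/25)) = shift / 1.414.

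| d (assumed) | shift at q = 13.5% | noncentrality | false-positive rate |
|---|---|---|---|
| 2 days | 0.27 days | 0.19 | 5.4% |
| 3 days | 0.40 days | 0.29 | 5.9% |
| 5 days | 0.67 days | 0.48 | 7.5% |

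**5. What a larger effect would need.** By the same formula, shifts of 1, 2 and 3 days give 10.7%, 28.3% and 54.7%. A 1-day shift needs q = 1/3 at d = 3, or q = 1/5 at d = 5. Under the step 3 assumptions, that requires a material share of the unscreened non-PAR mothers to be mothers who would also have failed.

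**6. Scale.** The Abstract expects LOS below 15 days against 25, a reduction of about 25 − 15 = 10 days. The largest shift in the table is 0.67 / 10 = 7% of that, or 0.67 / 4 = 17% of the 4-day difference used for power.

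**The case against.** The strongest reply is that the team's judgement is one gate among many. PAR personnel identify and first approach the mothers, and PAR officials judge compliance. DCF must have no known concerns, county and maternal dose-stability rules apply, a maternal UDS result can exclude, and the mother must consent. The words used for the screen also suggest that it comes before the infant's withdrawal is observed. A reader might infer that the unblinded team controls assignment. The documents do not support that: the team cannot place a non-PAR, non-compliant or unwilling mother on methadone.

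A reader might also take 1 − 25/39.3 = 36% as the share of comparators who failed the prescreen. That figure is the share of PAR dyads not entered, and its denominator is not the comparison group. On the pool the share is at most 13.5% under the stated assumptions.

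It is also fair to say that the design is openly non-randomised, that exclusion 7 removes some poor home situations, and that discharge while still on methadone builds a large LOS difference into the intervention.

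All of this limits the size, but the asymmetry remains. The veto applies to one group only, its content is undefined, and selecting approved mothers on one side biases the contrast even if no turned-down dyad crosses over. The historical comparison named in the primary objective does not escape, because the methadone group there is just as selected. Feasibility status is not an answer when comparing LOS is the primary objective and the test is powered.

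**Conclusion.** The point holds in a limited form. As written, the plan applies maternal compliance and suitability judgements to one group, lets dyads turned down under them enter the other, and tests LOS without adjustment. The expected direction favours methadone for LOS and for the maternal outcomes.

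The size cannot be derived from the documents. Through turned-down PAR dyads alone, with one year of accrual, comparators representative of the pool and an assumed 2 to 5 extra days, the shift is about 0.3 to 0.7 days and the false-positive rate 5.4% to 7.5%. With those assumptions, it is larger only if unscreened non-PAR mothers would also often fail the prescreen. Shifts in this range would not create or reverse a difference of about 10 days. They matter more if the observed difference is small, and for bonding and depression, where no expected effect is stated. This should be corrected, but it does not invalidate the study.

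**What to change.** 1. In inclusion 6, list the items that make a mother an adequate candidate. Record each decision and its reason, dated before delivery.
2. Add a comparison-group exclusion for dyads turned down under methadone inclusion 4 or 6. Keep mothers who merely declined methadone eligible, but flag them; they are arguably the closest comparators.
3. At consent, record the same objective maternal items for comparison mothers, for example PAR or other treatment-programme status, DCF concerns, county and UDS result. Do not ask the team whether a comparator would have passed: that would add a second discretionary choice after treatment has begun. PAR compliance also cannot be rated for non-PAR mothers. Pre-specify a sensitivity analysis of LOS, PBQ and EPDS restricted to, or adjusted for, these items.
4. Describe the LOS difference as the effect of the whole programme in selected mothers.

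The cost is a protocol amendment, one short form, a decision log, fewer eligible comparators and slightly less precision in the restricted analysis. The non-PAR pool of about 92 treated infants a year for 25 places gives some room, although that count is before the gestation, weight, custody and consent criteria. Reasons for turning a dyad down cannot be reliably reconstructed later, so the log should start at once.

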^e After initiation of methadone treatment and prior to discharge during the weaning phase of narcotic treatment

^f Home visit or phone interview

Principal Investigator: [name], MPH

Application Number: IRB00107690

Comparison Group:

Study Intervention	Enrollment	While inpatient	6 – 8 weeks of age
Informed Consent	X		
The Postpartum Bonding Questionnaire (PBQ)		X ^a	X ^b
Edinburgh Postnatal Depression Scale (EPDS)		X ^a	X ^b

^a After initiation of standard of care narcotics for treatment of NAS and prior to discharge during the weaning phase of narcotic treatment

^b Administered either through a home visit by Kids Home Care or via a phone interview conducted by a study team member

Routine (usual) care for infants born to mothers with a history of opiate use: All infants have routine scoring with the modified Finnegan scoring tool approximately every 3 to 4 hours per standard of care for signs of NAS. Infants will be managed with comfort, non-pharmacological measures. Initiation of medical treatment will take place when 2 consecutive Finnegan scores are > 8. Escalation of treatment and weaning will follow set protocols. Vital signs, blood pressures and cardiorespiratory monitoring follow the NICU standard of practice. Outpatient neurodevelopmental follow-up is offered at 1 and 2 years of age.

Comparison Group:

The comparison group of mother/baby dyads will receive standard of care treatment. The study interventions in this group are limited to the bonding and depression assessments. All other data required for analysis of the study aims can be abstracted from the baby's medical record as it is part of standard clinical care.

Methadone Treatment group:

A. Infant participants will receive the following services not part of the standard of care at JHACH:

- a) Initiation of the commercially available methadone treatment instead of morphine as pharmacologic treatment (see methadone treatment below);
- b) Maternal education on recognizing signs and symptoms of withdrawal as well as understanding and performing adequate Finnegan scoring. Specifically, mothers will be taught how to demonstrate tone and tremors on Physical exam.
- c) Provision of close psychological and emotional support to mothers

Principal Investigator: [name], MPH

Application Number: IRB00107690

- d) Facilitation of prolonged maternal physical presence at her infant's bedside

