JHACH admitted and average of 131 NAS infants in recent years who required pharmacological treatment for NAS. Approximately 30% of those mother/infant dyads were residents of PAR. We anticipate to enroll 25 mother/baby dyads into the methadone treatment group and 25 mother/baby dyads into the control group for a total of 100 participants. Both the mother and infant are research participants. Those infant participants are defined as 1) needing methadone or other opiate treatment, 2) transitioning to home care, and 3) successfully weaning off medication.

This number has been extrapolated taken into account the following projections/assumptions: 1) not all mothers staying at PAR will meet criteria for participation, and 2) polydrug use may be discovered at the time of delivery thus excluding from participation, and 3) 20-40% of infants enrolled may need adjunct second line therapy.

b. Blinding, including justification for blinding or not blinding the trial, if applicable.

This is a demonstration study with no blinding of subjects involved.

c. Justification of why participants will not receive routine care or will have current therapy stopped.

All infants will continue to receive routine hospital care. Methadone treatment is approved by the FDA, and endorsed by the AAP for inpatient and outpatient treatment of infants with NAS. While methadone is not used as the standard of care at JHACH NICU for infants with NAS at birth, it is still used for later iatrogenic withdrawal in the NICU and other intensive care units in the hospital.

d. Justification for inclusion of a placebo or non-treatment group. N/A Will need to justify this as a comparison groups has been included

e. Definition of treatment failure or participant removal criteria.

As delineated above, infants will be off-treatment from the demonstration project if 1) they require the addition of a second-line of pharmacological treatment or 2) they require re-admission to the

Principal Investigator: [name], MPH

Application Number: IRB00107690

hospital. Data will still be collected until final hospital discharge for these infants and the maternal assessments of bonding and depression will remain ongoing. .

Other Indications for participant off-study:

- a. Parent withdraws informed consent at any time
 - b. Infant transfers to another hospital.
 - c. Infant experiences an unexpected adverse event deemed related to study intervention

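### Maternal non-opiate drug use excludes infants from the methadone group but not from the comparison group, and LOS is compared without adjustment

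*Combined protocol and SAP*

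**What the plan says.** The study is non-randomised and open. Its primary objective (section 2) is to compare LOS in methadone-treated infants with historical data and with a concurrent group treated with another narcotic.

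Section 4 gives each group its own criteria. Both lists share the rules on gestation, birth weight, transfer within 72 hours, congenital anomalies, concomitant illness, adoption, pain requiring narcotics, and maternal hearing or language impairment. Methadone exclusion 5 removes "Infants whose maternal UDS at the time of delivery is positive for any other drug of abuse beside opiates". The comparison list has no such item. Its last exclusion, "Infants known upon admission who will be placed into state custody or sheltered", partly mirrors the methadone criterion on child-protection concerns, but says nothing about maternal drug use.

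The enrolment text (Eligibility and Enrollment Process, item b) describes comparators as NAS infants in the unit "who are started on treatment with a narcotic different than methadone, will be identified during the first week of NICU admission". No drug-screen condition is attached.

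The Accrual section expects the methadone rule to operate: "polydrug use may be discovered at the time of delivery thus excluding from participation". That sentence is one of the assumptions behind the enrolment number and creates no rule for comparators.

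Section 6.c compares LOS, bonding, depression, readmission and weight gain between groups with two-sample tests only. It specifies no adjustment, matching, restriction or sensitivity analysis.

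**The concern.** In a non-randomised comparison, eligibility rules are the main means of making the groups alike. Here one rule works the other way. It empties one group of infants whose mothers screened positive for non-opiate drugs and leaves them free to enter the other. If such exposure changes LOS, the observed difference is the treatment effect plus the effect of that case mix.

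The plan may also be unable to detect the problem afterwards. For comparators it names only the infant's chart as the source beyond the questionnaires ("All other data required for analysis of the study aims can be abstracted from the baby's medical record"), and maternal drug-screen status is not a named variable.

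Since the hypothesis is a stay under 15 days against 25, a false positive is not the main risk. The main risk is a distorted estimate of the LOS gain, with an interval around it that is too optimistic.

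**Working it through.** **Inputs from the documents.** Section 6.c: 25 dyads per group, SD 5 days in both, alpha 0.05, 80% power for a difference of more than 4 days, comparison mean about 25 days. Section 1: hypothesised LOS below 15 days against 25, so a difference of about 10 days. Two-sided testing is assumed, since the plan does not say.

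**The plan's own figure.** The standard error (SE) of the LOS difference is 5 × √(2/25) = 1.414 days. Power for 4 days is 80.7% by the normal approximation and 79.1% by the noncentral t distribution. The stated 80% reproduces.

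**Inputs not in the documents (assumed).** The share *p* of screen-positive comparison infants is taken as 10–60%, and their added stay *d* as 3–7 days. A zero or negative *d* is also possible: zero gives no bias, and a negative value reverses its direction.

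**Bias.** By design the methadone group has no screen-positive infants, so bias = *p* × *d*. The half-width of the 95% interval is t(0.975; 48 df) × 1.414 = 2.84 days. With no treatment effect, the chance of p < 0.05 comes from the noncentral t with noncentrality bias/1.414. Coverage is 100% minus that chance, and it does not depend on the true effect, because the bias simply shifts the interval.

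| p | d (days) | Bias (days) | Share of 10 days | p < 0.05 with no effect | 95% CI coverage |
|---|---|---|---|---|---|
| 10% | 3 | 0.3 | 3% | 5.5% | 94.5% |
| 20% | 3 | 0.6 | 6% | 7.0% | 93.0% |
| 30% | 3 | 0.9 | 9% | 9.6% | 90.4% |
| 40% | 5 | 2.0 | 20% | 28.3% | 71.7% |
| 60% | 7 | 4.2 | 42% | 82.9% | 17.1% |

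**Sensitivity to the SD.** The table takes SD 5 for each whole group, as the plan does. If 5 is instead the SD within each exposure stratum, the comparison SD is √(25 + p(1−p)d²). For 40% and 5 days this is 5.57, with coverage 74.2%. For 60% and 7 days it is 6.06 (SE 1.57), with coverage 25.5%. The low-end rows barely change.

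**Power if screen-positive comparators are dropped and not replaced.** With SE = 5 × √(1/25 + 1/n), power for 4 days is 79.1% at n = 25, 74.1% at n = 20, 66.5% at n = 15 and 54.6% at n = 10.

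**Pool of comparators.** The Accrual section gives an average of 131 pharmacologically treated NAS infants, about 30% of them Operation PAR dyads. Setting those aside leaves 131 × 0.7 = 91.7, about 92, before the other criteria and consent.

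**The case against.** The strongest objection is that this is one asymmetry among several. Only methadone-group mothers must be in Operation PAR's care, live in one of two counties, pass the team's prescreening and satisfy "Mother has been deemed by PAR officials as being compliant with the detoxification program" and "Mother has completed induction methadone treatment and has had no changes in medication dosage of 10% or greater in the two weeks preceding delivery". Nothing in the documents shows that non-opiate exposure matters more than these, and mending one line could make the groups look comparable when they are not. This stands as a limit on what the fix achieves. It does not excuse the drug-screen rule, which, unlike criteria tied to the programme, can readily be applied to comparators.

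Second, methadone infants go home while still on treatment, so most of the expected LOS difference comes from the discharge model, and the no-effect rejection rates describe a situation far from the one hoped for. That is fair, and coverage is the more relevant measure. Section 6.c plans tests and no interval, so coverage here describes the interval that would accompany the t-test.

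Third, the size is assumed throughout, and the worst case softens from 17.1% to 25.5% coverage under the within-stratum reading of the SD. Both points are correct; neither changes the conclusion.

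Finally, this is a feasibility study, and a restricted sensitivity analysis might suffice without changing eligibility. However, the concurrent LOS comparison is part of the primary objective. Recording status and adjusting for it would not work either, because the methadone group has no screen-positive dyads and so offers no overlap to adjust on.

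**Conclusion.** The concern holds. The one-sided exclusion and the unadjusted analysis are both plain in the text, and nothing elsewhere in the protocol restores comparability on this factor.

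Its size is not known. Under the assumed range the bias runs from 0.3 days, which is negligible, to 4.2 days, slightly more than the 4-day difference the study is sized to detect. If non-opiate exposure lengthens stay, the bias favours methadone; if it shortens stay, the bias goes the other way; if it has no effect, there is none. A true difference near 10 days would probably still be detected, but its estimate could be off by 3–42% of that figure. The change is cheap and should be made, though the flaw does not by itself invalidate the study.

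**What to change.** 1. Add methadone exclusion 5 to the comparison-group exclusions, record the maternal drug screen at delivery for comparison dyads, and fill the planned 25 comparison places with infants who meet the rule.
2. If screen-positive comparators are already enrolled, make the primary LOS comparison the one restricted to infants who meet exclusion 5, report the all-enrolled comparison as a sensitivity analysis, and restate the power if those infants are not replaced.
3. Any adjusted analysis should be secondary and use a variable that overlaps between groups, such as gestational age. With 25 per group it can carry few covariates.
4. State as a limitation that programme care, county residence, compliance, stable maternal dose and prescreening still apply to one group only.

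The cost is one eligibility line, one extra variable and wording in section 6.c. The maternal screen may need a source beyond the infant's chart. The comparison pool shrinks by an unknown amount from about 92. If 5, 10 or 15 comparators are lost without replacement, power for 4 days falls from 79% to 74%, 67% or 55%. The comparison with historical data is unchanged and keeps its own case-mix problem.
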